3. STUDY DESIGN

3.1 DESCRIPTION OF THE STUDY

Study CO39721 is a Phase Ib, open-label, multicenter, global study designed to evaluate the preliminary efficacy, safety, and pharmacokinetics of cobimetinib and atezolizumab when given to patients with $BRAF^{V600}$ WT metastatic or unresectable locally advanced melanoma who have progressed on a prior anti-PD-1 therapy. It is also designed to evaluate efficacy, safety, and pharmacokinetics of atezolizumab monotherapy in patients with $BRAF^{V600}$ WT metastatic or unresectable locally advanced melanoma who have not been previously treated. The co-primary endpoints of the study are ORR and DCR.

Approximately 102 patients with $BRAF^{V600}$ WT advanced melanoma who have progressed on a prior anti-PD-1 therapy will be enrolled in Cohorts A and B of this study (see [Figure 4](#)).

- Cohort A: Approximately 90 patients who have progressed on or after treatment with an anti-PD-1 agent will be enrolled.
- Cohort B (biopsy cohort): *Approximately* 12 patients will be enrolled in a mandatory biopsy cohort with inclusion according to the eligibility criteria specified in Section [4.1](#).

Approximately 50 patients who have not *received any prior anti-cancer treatment in the metastatic setting* will be enrolled in Cohort C.

Cohort A and B

[figure not shown]
All cycles will be 28 days in length for Cohorts A and B. Patients in Cohort A will begin dosing with cobimetinib and atezolizumab concurrently and will receive in all cycles 840 mg atezolizumab intravenous (IV) Q2W and 60 mg cobimetinib QD 21/7 (see [Figure 5](#)).

Patients in Cohort B (biopsy cohort) will also receive 60 mg cobimetinib QD 21/7 in all cycles. However, patients in this cohort will begin dosing with cobimetinib before atezolizumab and will receive 60 mg cobimetinib alone QD for the first 14 days of Cycle 1. Atezolizumab dosing (840 mg IV) will begin on Day 15, Cycle 1, and will continue thereafter at 840 mg IV Q2W. In Cycle 2 and all subsequent cycles, patients in this cohort will receive 60 mg cobimetinib QD 21/7 and 840 mg atezolizumab IV Q2W (see [Figure 6](#)).

Cohort C

[figure not shown]
All cycles in Cohort C will be 21 days in length. Patients in Cohort C will receive atezolizumab (1200 mg) Q3W (see [Figure 6](#)).

Figure 4 Study Schema

[figure not shown]
aPD-1 = anti-programmed cell death 1; ECOG = Eastern Cooperative Oncology Group; PD = progressive disease; PS = performance score; RECIST = Response Evaluation Criteria in Solid Tumors.

Figure 5 Treatment and Biopsy Schedule (Cohort A)

[figure not shown]
D = day; IV = intravenous; PO = by mouth.

Figure 6 Treatment and Biopsy Schedule (Cohort B)

D= day; IV= intravenous; PO= by mouth.

Figure 7 Treatment and Biopsy Schedule (Cohort C)

D= day; IV= intravenous.

After signing informed consent, eligible patients will undergo screening procedures that include testing for the *BRAF*^{V600} mutation; laboratory tests; 12-lead ECGs; left ventricular function evaluation (LVEF; echocardiogram [ECHO] or multiple-gated acquisition [MUGA] scan); contrast-enhanced brain computed tomography (CT) scan or magnetic resonance imaging (MRI); contrast-enhanced CT or MRI scan of the chest, abdomen, and pelvis; and ophthalmologic (for Cohorts A and B) and dermatologic assessments.

All patients will be closely monitored for safety and tolerability throughout the study. The National Cancer Institute Common Terminology Criteria for Adverse Events, Version 4.0 (NCI CTCAE v4.0) will be used to characterize the toxicity profile of the study treatments for all patients. The protocol includes a detailed risk management plan for monitoring and managing molecule-specific and potential combination toxicities (see Section 5).

For all cohorts, tumor response will be evaluated by the investigator according to RECIST v1.1 (see Appendix 3); immune-modified RECIST v1.1 (see Appendix 4) will also be assessed by the investigator. For Cohort C, tumor response will also be determined by the independent review committee (IRC) according to RECIST v1.1. All measurable and non-measurable lesions will be documented at screening. Response will be assessed at 8-week intervals until investigator-determined disease progression (according to RECIST v1.1), death, or initiation of subsequent anti-cancer therapy, whichever occurs first. Patients who experience disease progression must have scans repeated 4 weeks after initial documentation of progression to confirm disease progression. Tumor assessments are to continue according to schedule in patients who discontinue treatment for reasons other than confirmed disease progression, unless subsequent anti-cancer therapy is initiated.

Study treatment will continue for all patients until investigator-determined disease progression (confirmed 4 weeks later, for clinically stable patients with a favorable benefit-risk assessment), death, unacceptable toxicity, or pregnancy, whichever occurs first. Patients in Cohorts A and B who discontinue one study drug may be able to continue the remaining study drug per guidelines for management of specific adverse events provided in Table 5.

Clinically stable patients who have a favorable benefit-risk assessment may continue on study treatment following radiographic progression per RECIST v1.1. Approval from study medical monitor must be obtained prior to continuing treatment. Patients who continue treatment beyond radiographic disease progression will be closely monitored.

After treatment discontinuation, patients will be followed for disease progression if applicable and followed for survival until death, withdrawal of consent, or loss to follow-up, whichever occurs first.

3.1.1 Biopsies and Archival Tissue

Biomarker assessments on tumor biopsy tissue are an important part of this study and will be used to elucidate mechanisms of resistance to anti-PD-1/anti-PDL-1 therapy as well as to evaluate the effects of atezolizumab monotherapy and cobimetinib-atezolizumab combination therapy on tumor immune contexture. All patients must provide archival (< 5 years old) tissue or a fresh biopsy before treatment start.

3.1.1.1 Optional Biopsies (Cohort A)

Patients in Cohort A will be requested, via separate optional consent, to provide biopsies (core needle [minimum three cores and minimum diameter 18 gauge; 16 gauge is preferable] or excisional biopsy) for the study of pharmacodynamic changes related to the activity of cobimetinib and atezolizumab. For patients who consent to biopsies, a predose specimen will be obtained after eligibility criteria have been fulfilled before Cycle 1, Day 1, only if archival tissue (< 5 years old) was provided for the *BRAF* WT testing. Predose specimens are not required for patients who provide a fresh biopsy before treatment start. A subsequent biopsy will be performed 4–6 weeks after the first atezolizumab dose. An additional biopsy may be collected per investigator discretion, preferably at the time of radiographic progression or response.

3.1.1.2 Mandatory Biopsies (Cohort B)

Patients enrolled in Cohort B, the biopsy cohort, must have at least two (preferably three) accessible lesions that meet the requirements specified in the eligibility criteria.

Exceptions may be made if patient has only one lesion that allows multiple biopsies following discussion with Medical Monitor. One pretreatment, up to two on-treatment biopsies, and one post-progression biopsy will be performed. If more than one biopsy will be obtained from one lesion, the lesion should be large enough to permit successive biopsies ≥ 1 cm apart. Investigators are strongly encouraged to obtain two on-treatment biopsies as described below; at a minimum, the Day 10–14 biopsy should be obtained to test for possible immunologic effects of cobimetinib alone.

Patients in the biopsy cohort will undergo biopsies according to the following schedule:

- A predose biopsy will be taken before Day 1, Cycle 1. (The predose biopsy is not required if a fresh biopsy was provided during screening).
- On Day 1, Cycle 1, patients will start treatment with cobimetinib alone.
- A mandatory on-treatment biopsy will be obtained between Days 10 and 14 of Cycle 1.
- Patients will receive their first atezolizumab dose on Day 15 of Cycle 1.
- A second, optional, on-treatment biopsy will be obtained during Cycle 2, 4–6 weeks after the first dose of atezolizumab to assess the combined effects of cobimetinib and atezolizumab.
- A mandatory, post-treatment biopsy will be obtained at the time of radiographic progression.

Patients in tumor biopsy cohorts whose tissue sample is not evaluable may receive study treatment, but these patients may be replaced for the purpose of serial biopsy assessment.

If a patient undergoes a medically indicated procedure at any time during the study that has the likelihood of yielding tumor tissue, any remaining samples or a portion of the tumor sample not necessary for medical diagnosis may be obtained for exploratory analysis. Patients must have provided specific consent in order for discarded samples from routine care to be obtained.

3.1.1.3 Optional Biopsies (Cohort C)

Patients in Cohort C are required to provide archival tissue or fresh biopsy during screening. They will be requested to provide optional fresh biopsies (core needle [minimum three cores and minimum diameter 18 gauge; 16 gauge is preferable] or excisional biopsy) for the study of tumor immune contextures related to activity or resistance of atezolizumab. For patients who consent to biopsies, a predose specimen will be obtained after eligibility criteria have been fulfilled before Cycle 1, Day 1, unless a fresh biopsy was provided during screening. An additional biopsy is requested to be collected at the time of radiographic progression.

A schedule of activities is provided in [Appendix 1](#).

3.1.2 Dosing of Study Treatment beyond Disease Progression

Dosing of study treatment beyond RECIST v1.1–defined disease progression is allowed for patients in all treatment arms.

Atezolizumab will be administered by IV infusion at a fixed dose of 840 mg Q2W (Cohorts A and B) and 1200 mg IV Q3W (Cohort C) until unacceptable toxicity or loss of clinical benefit, as determined by the investigator, after an integrated assessment of radiographic and biochemical data, local biopsy results (if available), and clinical status (e.g., symptomatic deterioration such as pain secondary to disease). Due to the possibility of an initial increase in tumor burden caused by IC infiltration in the setting of a T-cell response (termed pseudoprogression) with atezolizumab treatment, radiographic progression per RECIST v1.1 may not be indicative of true disease progression. In the absence of unacceptable toxicity, patients who meet criteria for disease progression per RECIST v1.1 while receiving atezolizumab will be permitted to continue atezolizumab if they meet all of the following criteria:

- Evidence of clinical benefit, as determined by the investigator following a review of all available data
- Absence of symptoms and signs (including laboratory values, such as new or worsening hypercalcemia) indicating unequivocal progression of disease
- No decline in Eastern Cooperative Oncology Group (ECOG) Performance Status that can be attributed to disease progression
- Absence of tumor progression at critical anatomical sites (e.g., leptomeningeal disease) that cannot be managed by protocol-allowed medical interventions

- Patient's written consent to acknowledge deferring other treatment options in favor of continuing study treatment at the time of initial disease progression
- Approval by the Medical Monitor

3.2 END OF STUDY AND LENGTH OF STUDY

The study will end when all patients enrolled have been followed until death, have withdrawn consent, have been lost to follow-up, or when the Sponsor decides to end the trial, whichever occurs first. The total length of the study, from first patient in until end of follow-up, is expected to be approximately 4 years.

3.3 RATIONALE FOR STUDY DESIGN

3.3.1 Rationale for Cobimetinib plus Atezolizumab Dose and Schedule

Concomitant administration of cobimetinib and atezolizumab was studied in Phase Ib Study GP28363 (Section 1.3.5). Cobimetinib and atezolizumab in combination were found to be safe and tolerable with an atezolizumab dose of 800 mg IV Q2W (equivalent to the approved dose and schedule for treatment of bladder cancer of 1200 mg IV Q3W) and cobimetinib on the approved dose and schedule of 60 mg QD 21/7.

Atezolizumab was administered as a single agent in Study PCD4989g with encouraging efficacy and safety outcomes at doses equivalent to the approved dose and schedule for treatment of bladder cancer of 1200 mg IV Q3W (Section 1.3.2). Simulations using a population PK model for atezolizumab demonstrate that at the dose of 840 mg IV Q2W (atezolizumab dose schedule in Arm A and Arm B) provides an exposure within the range typically seen for the 1200 mg IV Q3W dose (Arm C atezolizumab dose schedule). Observed Phase 1 data after Q2W administration was consistent with popPK simulated profiles providing confidence in the predictability of the simulations. Based on the data available, the two dose schedules are expected to be comparable in safety and efficacy.

3.3.1.1 Cohort A (Cobimetinib plus Atezolizumab with Concurrent Start)

Cobimetinib will be given at the approved dose and schedule of 60 mg QD 21/7. For administration with cobimetinib on this 28-day cycle, a dose of 840 mg atezolizumab will be given Q2W. The 840-mg dose is expected to be similar to the 800-mg dose of atezolizumab and was selected in this study to simplify dose administration.

Atezolizumab is formulated at a concentration of 60 mg/mL; thus, 800 mg corresponds to a volume of 13.33 mL. To ensure consistent, precise, and clinically feasible administration in this study, the volume was rounded up to 14 mL, corresponding to a dose of 840 mg. The 840-mg dose is not expected to result in meaningfully different exposures compared with an 800-mg dose.

In addition, the atezolizumab dose of 840 mg Q2W is equivalent to an average body weight–based dose of 15 mg/kg Q3W, the Phase II dose for atezolizumab derived from nonclinical and clinical studies. It has been used in multiple atezolizumab Phase III studies in other indications.

3.3.1.2 Cohort B (Biopsy Cohort)

Cohort B is designed to allow assessment of the effects of cobimetinib on immune therapy. In this cohort, in Cycle 1 only, cobimetinib will be given for 14 days before initiation of atezolizumab treatment as described in Section 3.1. Biopsies obtained before treatment start and at the end of the 14-day cobimetinib monotherapy period will allow elucidation of the effects of cobimetinib on tumor immune contexture. Additional biopsies taken during the combination treatment period and at radiographic progression will support evaluation of the effects of combination treatment on the tumor micro-environment and the identification of potential mechanisms of resistance to combination therapy.

During Cycle 2 and all subsequent cycles, patients in Cohort B will receive cobimetinib 60 mg QD 21/7 and atezolizumab 840 mg IV Q2W, the same dose and schedule as in Cohort A.

3.3.1.3 Cohort C (Atezolizumab Monotherapy Cohort)

Atezolizumab will be administered at a dose of 1200 mg IV Q3W. As detailed in Section 3.3.1, this approved dose schedule based on average body weight results in similar atezolizumab exposure after the 840 mg Q2W dose schedule.

3.3.2 Rationale for Patient Population and Cohorts

3.3.2.1 Cohort A (Cobimetinib plus Atezolizumab with Concurrent Start)

Cohort A will enroll patients with advanced *BRAF*^{V600} *WT* melanoma whose disease has progressed on or after treatment with an anti–PD-1 agent. This patient population has limited treatment options and high unmet need. The known effects of MAPK inhibitors, including cobimetinib, on tumor microenvironment (see Section 1.3.4), include effects that may enable conversion to an immunoresponsive phenotype, sensitize refractory tumors to anti–PD-1/PD-L1 agents, and/or re-sensitize relapsed tumors to these agents, and suggest that combination therapy with cobimetinib and atezolizumab may be efficacious in this population. This hypothesis is supported by clinical data from Study GP28363 (see Section 1.3.5) which indicate that combination therapy with cobimetinib and atezolizumab in advanced melanoma results in improved ORR and PFS relative to either PD-1/PD-L1 or MEK inhibitor monotherapy.

3.3.2.2 Cohort B (Biopsy Cohort)

The molecular mechanisms of primary and secondary resistance to anti–PD-1/PD-L1 therapies and effects of cobimetinib on the tumor microenvironment in patients with post–PD-1 progression require further elucidation to inform optimal development of combination therapy. In order to ensure that biomarker data collected from biopsies are

optimally informative, patients enrolled in Cohort B are required to fulfill additional eligibility criteria that define their disease as true primary or secondary resistant.

In order to ensure that patients have received sufficient anti-PD-1 therapy to adequately assess the tumor's sensitivity, and that the tumor's current molecular profile represents the molecular profile at progression, all patients in this cohort must have received a minimum of two cycles of the anti-PD-1 agent and must have progressed on or after this therapy within 12 weeks before study start.

The cohort will enroll *approximately* 6 patients with primary resistance, defined as progressive disease (PD) as best response, according to RECIST v1.1, and *approximately* 6 patients with secondary resistance, defined as PD following initial confirmed response according to RECIST v1.1.

3.3.2.3 Cohort C (Atezolizumab Monotherapy)

Cohort C will enroll approximately 50 patients with advanced $BRAF^{V600}$ WT melanoma, who have not received previous treatment, to receive atezolizumab monotherapy.

Data from Study PCD4989g indicate that atezolizumab monotherapy provides efficacy benefit in advanced melanoma comparable with that reported for approved aPD-1 monotherapies and has a comparable safety profile (Section 1.1.2). However, since the patient population in this study was heterogeneous with respect to line of therapy and $BRAF^{V600}$ status, evaluation of atezolizumab monotherapy in previously untreated, $BRAF$ WT melanoma, will allow more accurate understanding of the achievable magnitude of efficacy in this population. In addition, this cohort will allow comparison of the potential molecular mechanisms of resistance between the 3 cohorts.

In all Cohorts A, B and C, inclusion criteria require that $BRAF^{V600}$ WT status has been confirmed using an approved clinical test.

In order to ensure that the ORR, DCR, duration of response (DOR), and PFS can be adequately assessed, patients must have measurable disease (per RECIST v1.1.) and locally advanced, unresectable or metastatic melanoma, as defined by the American Joint Committee on Cancer classification, Version 7 (Balch et al. 2009).

Additional eligibility criteria have been incorporated that are pertinent to the safety profiles for cobimetinib and atezolizumab (and PD-L1-targeted therapies as a therapeutic class). These criteria have been informed by clinical experience in Study GP28363, the Phase Ib study, which evaluates the combination of cobimetinib and atezolizumab in patients with diverse solid tumors, including advanced melanoma.

3.3.3 Rationale for Primary Endpoint Selection

This study is designed to gain preliminary information on the potential for efficacy of atezolizumab in combination with cobimetinib in $BRAF^{V600}$ WT melanoma that has

progressed on or after treatment with an anti-PD-1 therapy and will initially enroll a limited number of patients (n=42). Compelling evidence of anti-tumor activity in these patients will result in further evaluation of the combination's activity in this indication

The study will also enroll an additional cohort of patients with *BRAF*^{V600} WT melanoma who have not been previously treated to obtain additional efficacy and safety data for atezolizumab as monotherapy. This will extend the efficacy data seen in melanoma in Study PCD4989g and clarify the magnitude of benefit achievable in previously untreated *BRAF*^{V600} WT patients.

The co-primary endpoints for this study are ORR and DCR at 16 weeks.

ORR is recognized as a correlate of survival in advanced melanoma and has been used as a primary endpoint in a pivotal study in this indication (Weber et al. 2015). DCR at 16 weeks is included as a co-primary efficacy endpoint because clinical experience in Study GP28363 indicates that early evaluations of ORR may underestimate the percentage of patients who benefit from the combination. In Study GP28363, of the 9 melanoma patients with a PR, 3 patients had prolonged SD and converted from SD to a PR after > 12 months of therapy. Further, in a recent retrospective study that included 172 metastatic melanoma patients treated with high-dose IL-2, SD and DCR were found to correlate well with survival (Hughes et al. 2015). Early compelling evidence of anti-tumor activity, based on a high DCR rate, will allow timely initiation of further evaluation of the combination.

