Approximately 102 patients with *BRAF*^{V600} WT advanced melanoma who have progressed on a prior anti-PD-1 therapy will be enrolled in Cohorts A and B of this study.

- Cohort A: Approximately 90 patients who have progressed on or after treatment with an anti-PD-1 agent will be enrolled.

- Cohort B (biopsy cohort): *Approximately 12 patients will be enrolled in a mandatory biopsy cohort*

Approximately 50 patients who have not *received any prior anti-cancer treatment in the metastatic setting* will be enrolled in Cohort C.

Target Population

Inclusion Criteria

Patients must meet the following criteria for study entry:

Disease-Specific Inclusion Criteria: Cohorts A and B

- Histologically confirmed Stage IV (metastatic) or unresectable Stage IIIc $BRAF^{V600}$ WT (locally advanced) melanoma
- Documentation of $BRAF^{V600}$ mutation–negative status in melanoma tumor tissue (archival [< 5 years old] or newly obtained) through use of a clinical mutation test approved by the local health authority (e.g., U.S. Food and Drug Administration [FDA]-approved test, CE-marked [European conformity] in vitro diagnostic in E.U. countries, CLIA-certified NGS test, or equivalent)
- Measurable disease according to Response Evaluation Criteria in Solid Tumors Version 1.1 (RECIST v1.1)
- Disease progression during or after treatment with a PD-1 inhibitor either as monotherapy or in combination with other agent(s)

Additional Disease-Specific Inclusion Criteria in Cohort B (Biopsy Cohort)

- Patients in this cohort must have progressed during or after anti-PD-1 therapy within 12 weeks before study start.
- Patients in this cohort must have received a minimum of two cycles of anti-PD-1 therapy.
- Patients in this cohort must meet criteria for primary ($n = 6$) or secondary ($n = 6$) resistance to an anti-PD-1 agent as outlined below:
 - Primary resistance is defined as progressive disease, according to RECIST v1.1, as best response.
 - Secondary resistance is defined as progressive disease after initial confirmed response according to RECIST v1.1,
- Patients in this cohort must consent to undergo tumor biopsies of accessible lesions before and during treatment and at radiographic progression for biomarker analyses.

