Atezolizumab will be supplied by the Sponsor as sterile liquid in 20-mL glass vials. The vial is designed to deliver 20 mL (1200 mg) of atezolizumab solution but may contain more than the stated volume to enable delivery of the entire 20-mL volume. For Cohorts A and B, extraction of 14 mL of atezolizumab solution from a 1200 mg vial contains an 840-mg dose.

Cohort A: Patients will initiate dosing with atezolizumab concurrently with cobimetinib and will receive atezolizumab 840 mg intravenously Q2W on Days 1 and 15 of all cycles.

Cohort B: Patients will receive the first dose of atezolizumab at 840 mg intravenously on Day 15 of Cycle 1. Thereafter, they will receive atezolizumab 840 mg intravenously Q2W on Days 1 and 15 of Cycle 2 and all subsequent cycles.

Cohort C: Patients will receive atezolizumab 1200 mg intravenously Q3W as monotherapy.

Statistical Methods

Primary Analysis

The primary analysis will be conducted *in Cohorts A and B approximately 24 weeks after the last patient is enrolled in Cohort A. At this time, Cohorts A and B will have a minimum follow up of approximately 24 weeks. The primary analysis for Cohort C may be analyzed independently, with a minimum of 24 weeks follow up for patients in Cohort C.* Both separate and pooled efficacy and safety analyses will be performed on Cohorts A and B given their similar patient populations. Additional tumor immunology and biomarker analyses will also be conducted on Cohort B. Study data will be described and summarized for Cohort C separately.

Determination of Sample Size

This study is designed for hypothesis generation with the intention to provide an informative evaluation on the selected efficacy endpoints. No formal inferential testing is planned. Approximately 152 patients are anticipated to be enrolled, with *approximately* 90 patients in Cohort A, 12 patients in Cohort B, and 50 patients in Cohort C.

A combined 102 patients in Cohorts A and B allows for a robust comparison against historical control of ipilimumab and chemotherapy in patients who have previously progressed on anti-PD1 therapy, which generally have response rates of less than 17%. For example, with 102 patients in Cohorts A and B, observing 26 patients with objective response corresponds to ORR (95% CI) of 25.5% (17.4%, 35.1%) and observing 60 patients with disease control corresponds to a DCR (95% CI) of 58.8% (48.6%, 68.5%).

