4. MATERIALS AND METHODS

4.1 PATIENTS

Approximately 102 patients with advanced melanoma who have progressed on or after prior treatment with an anti–PD-1 therapy will be enrolled in Cohorts A and B.

An additional 50 patients with advanced melanoma who have not received previous treatment will be enrolled in Cohort C.

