6. STATISTICAL CONSIDERATIONS AND ANALYSIS PLAN

This study evaluates the preliminary efficacy, safety, and pharmacokinetics of atezolizumab plus cobimetinib in patients with *BRAF*^{V600} WT metastatic or unresectable locally advanced melanoma who have progressed on prior anti-PD-1 therapy (Cohorts A and B), and atezolizumab monotherapy in patients with *BRAF*^{V600} WT metastatic or unresectable locally advanced melanoma who have not been previously treated (Cohort C).

The primary analysis will be conducted *in Cohorts A and B approximately 24 weeks after the last patient is enrolled in Cohort A. At this time, Cohorts A and B will have a minimum follow up of approximately 24 weeks. The primary analysis for Cohort C may be analyzed independently, with a minimum of 24 weeks follow up for patients in Cohort C.* Both separate and pooled efficacy and safety analyses will be performed on Cohorts A and B, given their similar patient populations. Additional tumor immunology and biomarker analyses will also be conducted on Cohort B. Study data will be described and summarized for Cohort C separately.

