6.1 DETERMINATION OF SAMPLE SIZE

This study is designed for hypothesis generation with the intention to provide an informative evaluation on the selected efficacy endpoints. No formal inferential testing is planned. Approximately 152 patients are anticipated to be enrolled, with *approximately 90 patients in Cohort A, 12 patients in Cohort B, and 50 patients in Cohort C.*

A combined 102 patients in Cohorts A and B allows for a robust comparison against historical control of ipilimumab and chemotherapy in patients who have previously progressed on anti-PD1 therapy, which generally have response rates of less than 17%. For example, with 102 patients in Cohorts A and B, observing 26 patients with objective response corresponds to ORR (95% CI) of 25.5% (17.4%, 35.1%) and observing 60 patients with disease control corresponds to a DCR (95% CI) of 58.8% (48.6%, 68.52%).

Enrolling 50 patients in Cohort C provides reasonably reliable estimates of the ORR and DCR in patients who have not been previously treated to allow for an accurate understanding of the achievable magnitude of efficacy in this population.

For example, observing 17 patients with objective response corresponds to ORR (95% CI) of 34.0% (21.1%, 48.8%) and observing 32 patients with disease control corresponds to DCR (95% CI) of 64% (49.2%, 77.1%). Enrolling 50 patients in Cohort C also provides an opportunity to explore the preliminary efficacy in relevant patient subgroups including biomarker subgroups defined by PD-L1 expression.

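### Does the figure of 42 patients in Section 3.3.3 mean that Cohorts A and B grew to about 102 because of early results?

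*Combined protocol and SAP*

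**What the plan says.** Section 3.3.3, which explains the choice of co-primary endpoints, states that in post-anti-PD-1 disease the study "will initially enroll a limited number of patients (n=42). Compelling evidence of anti-tumor activity in these patients will result in further evaluation" of the combination in this indication. Later in the same section, the paragraph defending DCR as a co-primary endpoint says that early evidence "based on a high DCR rate, will allow timely initiation of further evaluation of the combination".

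Every passage that sets a number gives a different one:

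- Section 3.1: "Approximately 90 patients who have progressed on or after treatment with an anti-PD-1 agent will be enrolled" in Cohort A, plus about 12 in Cohort B. The synopsis gives the same figures.
- Section 4.1: "Approximately 102 patients with advanced melanoma who have progressed on or after prior treatment with an anti"-PD-1 therapy, in Cohorts A and B together.
- Section 6.1: "A combined 102 patients in Cohorts A and B allows for a robust comparison against historical control of ipilimumab and chemotherapy", with the example that "observing 26 patients with objective response corresponds to ORR (95% CI) of 25.5% (17.4%, 35.1"%).
- Section 9.4: about 152 patients in all, including Cohort C.

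Section 6 plans one primary analysis of Cohorts A and B, "approximately 24 weeks after the last patient is enrolled in Cohort A". Section 6.9 permits optional interim efficacy analyses by the sponsor's team and requires the decision and the timing to be recorded in the trial master file beforehand. Section 6.1 says that the study generates hypotheses and that no formal test is planned.

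**The concern.** A reader who meets 42 in one section and 102 in the others will ask what happened in between. Section 3.3.3 speaks of an initial group, and of further evaluation if that group does well. That can be read as a two-stage design whose second stage opened only after good results.

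If so, the pooled ORR and DCR would be conditional on a favourable first stage and would overstate the true rates. ORR and DCR are the co-primary endpoints, and the pooled 102 patients are the set that Section 6.1 compares with historical response rates below 17%. No separate estimate for the first 42 is planned, so the bias would not be visible in the reported results. The optional interim analyses in Section 6.9 add to the unease, because they leave room for an early look at efficacy.

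**Working it through.** **1. Do the operative numbers agree?** From Sections 3.1 and 6.1: 90 + 12 = 102 for Cohorts A and B, and 102 + 50 = 152 with Cohort C, as Section 9.4 states. The other sums are 90 + 50 = 140 and 12 + 50 = 62. None of 90, 12, 50, 62, 102, 140 or 152 equals 42, so the figure in 3.3.3 belongs to no part of the current plan.

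**2. Which number does the statistical section use?** Exact (Clopper-Pearson) 95% limits reproduce the plan's own examples:

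- 26/102 = 25.5% (17.4%, 35.1%)
- 60/102 = 58.8% (48.6%, 68.5%)

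A similar ORR in 42 patients would be 11/42 = 26.2% (13.9%, 42.0%), which includes 17%. At n = 42 the lower limit first exceeds 17% at 13/42 = 31.0% (17.6%, 47.1%). Section 6.1 is therefore built on 102, and 42 plays no part in it.

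**3. What would a results-driven increase have done?** The documents state no rule, so the thresholds here are assumptions. Suppose enrolment continued from 42 to 102 (60 more patients) only if at least t of the first 42 succeeded. With X ~ Binomial(42, p),

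bias = (E[X | X ≥ t] + 60p)/102 − p.

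For example, with p = 26/102 and t = 10, E[X | X ≥ 10] = 12.28, and (12.28 + 15.29)/102 − 0.2549 is about 0.015, or 1.5 points.

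| Endpoint, assumed true rate | t of 42 | Chance of continuing | Bias in pooled rate, points |
|---|---|---|---|
| ORR 25.5% | 8 / 10 / 12 | 87% / 66% / 38% | +0.6 / +1.5 / +2.8 |
| ORR 17% | 8 / 10 / 12 | 42% / 17% / 4% | +2.2 / +3.8 / +5.5 |
| DCR 58.8% | 21 / 25 / 27 | 91% / 53% / 29% | +0.6 / +2.4 / +3.7 |

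For scale, the interval for 26/102 reaches 25.5 − 17.4 = 8.1 points below the estimate and 35.1 − 25.5 = 9.6 above. The interval for 60/102 reaches about 10 points each way. At the plan's example rates the bias stays well inside those margins, and its larger values need thresholds that would be met in well under half of trials. The 17% row is less comfortable, but strict thresholds would then seldom be met.

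**4. Is there any sign that such a rule existed?** No section describes a first stage, a pause in enrolment, a threshold or a decision to expand. The DCR sentence in 3.3.3 mentions neither the 42 patients nor enrolment; it argues for DCR as an endpoint. Further evaluation of the combination in the indication reads at least as naturally as later work. The typography gives a weak hint of age: the amendment summary says that substantive new text is in italics, yet the 102 in the sample size sections and the 90 in Section 3.1 are in plain type, which suggests that the enlargement came before Version 5. This is not conclusive, because the cohort list in Section 6.1 is itself in italics.

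**The case for a change.** The strongest reply is that silence does not show absence. Section 3.3.3 twice links early activity to further evaluation, the second time through a co-primary endpoint, and the documents never say why 42 became 102. The word approximately cannot bridge the two numbers. If the increase did follow from results, a reader comparing the pooled ORR with 17% would be misled without knowing it, and one sentence from the sponsor would settle the matter.

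Part of this stands. The number in 3.3.3 is wrong for the current plan, and the supplied text does not rule out a results-driven increase. The opening of the amendment summary and the rationales for earlier amendments were not available to me, so an explanation may exist there.

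The rest does not carry a change. Reporting the first 42 and the later patients separately would be useful only under a reading that no passage supports, and it would cost precision. A formal early look would have to be recorded in the trial master file before it took place (Section 6.9), so it should leave a dated trace, though not a public one. It is also fair to say that Section 6.1's description of the historical comparison as robust is generous: 26 is the smallest count of 102 whose lower limit exceeds 17% (25/102 gives 16.5%). That is a matter of tone. The interval is correct and no test depends on it.

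**Conclusion.** This is a clerical slip. The 42 agrees with nothing else in the plan, and the simplest reading is text not updated after the study was enlarged. The enrolment target (about 102), the efficacy analysis set (all patients who receive at least one dose, Section 6.4), the precision statements and the timing of the primary analysis are each stated without ambiguity, and none refers to 42. Correcting the number would tidy the rationale but would not alter what is done, estimated or concluded.

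If the 42 is leftover text, or if further evaluation means a later study, the bias is zero. The non-zero figures in the table hold only if enrolment grew because of results, under thresholds that I assumed. The conclusion rests on the documents as supplied; a record showing that the increase was conditional on early response or disease control would reopen the question.
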